### **5.1.6. Additional Reference Timepoints**

Three additional Reference Timepoints (RTs) will be used for additional analyses of selected efficacy endpoints.

The PegIFN RT is defined as the last observed non-missing measurement before the first PegIFN- $\alpha$ 2a for Arm 2. This RT will be used for additional analyses for selected efficacy endpoints after Week 12 of treatment period and FU phase.

The NA RT is defined as the last observed non-missing measurement before the start of FU phase for participants who met the NA completion criteria at the EOT. This RT will be used for additional analyses for selected efficacy endpoints for FU phase.

The JNJ-3989 RT is defined as the last observed non-missing measurement at the time of stopping JNJ-3989. This RT will be used for additional analyses for selected efficacy endpoints for FU phase.

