6.5.1. NA Treatment Completion

All participants will receive the last dose of JNJ-3989 at Week 24 and the last dose of PegIFN- α 2a at Week 23 (Arms 1 and 2) or Week 11 (Arm 3). They will start the FU Period after the Week 24 visit. If all of the following NA treatment completion criteria are met based on the Week 24 results, treatment with NA will be stopped at the next scheduled visit (ie, FU Week 2):

- The participant has ALT <3x ULN, AND
- The participant has HBV DNA <60 IU/mL at Week 24 and HBV DNA <LLOQ at the previous visit, or HBV DNA <LLOQ at Week 24, AND
- The participant is HBeAg-negative, AND
- The participant has HBsAg <100 IU/mL.

Note: Participants who are close to meeting the protocol-defined NA treatment completion criteria with the Week 24 results, and do meet the criteria based on the FU Week 2 results may be allowed to stop NA at FU Week 4, after consultation with the Sponsor. In case of ALT elevation \geq 3x ULN at Week 24, the investigator must consider different potential causes of increased ALT to ensure appropriate work up and management as needed. If the ALT elevation is unrelated to HBV activity and/or <3x ULN by FU Week 2, NA completion may be considered at the discretion of the investigator and in consultation with the sponsor.

Participants who do not meet the above criteria based on the Week 24 or FU Week 2 results should continue NA treatment during the 48-week FU Period.

Participants who meet the above-mentioned NA treatment completion criteria will be monitored closely during the 48-week FU Period with a study visit at least once every 4 weeks. NA treatment should be re-started in accordance with the NA re-treatment criteria (see Section [6.5.2](#), NA Re-treatment Criteria During Follow-up, for more details).

The investigator should consider to re-start NA treatment per local standard of care at the EOS visit (Follow-up Week 48) for participants who met the NA treatment completion criteria based on the Week 24 (or FU Week 2) results, who did not re-start NA treatment during the follow-up phase, and who did not achieve and maintain HBsAg seroclearance. NA will not be provided by the sponsor after the final study visit.

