**Table 3: Analysis Phases Start and End Dates**

Analysis Phase	Start Date	End Date
Screening	The date of signing the informed consent	1 day before the first study agent intake
Treatment period	Date of first study agent intake	
If participant did not withdraw from the study and did not discontinue treatment early prior to the projected/actual Week 24 Visit date:
 
Min [Date of Week 24 study agent intake – 1 day, cut-off dateb]
 
Otherwise:
 
Max [Early study withdrawal visit date, study agent discontinuation date] + 5 daysa or cut-off dateb, whichever occurs first

Follow-up	
Participants who did not withdraw informed consent during treatment period: End of treatment period + 1 day
 
Otherwise: missing
	Max [study discontinuation date, study completion date] or cut-off date b , whichever occurs first

a Addition of 5 days is only applicable for Adverse Events and Concomitant Medications.

b Cut-off dates will be defined to match the prespecified timepoints for DRC safety monitoring, interim analyses, the primary and the final analyses, respectively.

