## **5.4.1.2. Continuous Endpoints**

### **5.4.1.2.1. HBsAg, HBeAg, HBV DNA and ALT**

Actual values (original unit and  $\log_{10}$  transformed values), changes from baseline ( $\log_{10}$  transformed values) and change from RTs over time in HBsAg, HBeAg, HBV DNA and ALT (actual values only) will be evaluated.

Change from baseline is defined as the value at a given time point minus baseline value.

The change from baseline value to the nadir (i.e. maximum decrease for each participant) in HBsAg, HBeAg, and HBV DNA will be evaluated at 3 intervals: on-treatment nadir (first 24 weeks), during follow-up nadir, and entire study nadir.

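### The SAP's NA reference timepoint falls a planned 2 weeks before NA stops (6 weeks by Table 3 dates) and leaves out participants who qualify at FU Week 2

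*SAP*

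**What the plan says.** SAP 5.1.6 sets up three reference timepoints. The NA RT is the "last observed non-missing measurement before the start of FU phase for participants who met the NA completion criteria at the EOT". Its stated use is general: "This RT will be used for additional analyses for selected efficacy endpoints for FU phase". The JNJ-3989 RT is the "last observed non-missing measurement at the time of stopping JNJ-3989", and the PegIFN RT is the last value before the first PegIFN-α2a dose in Arm 2. The RTs feed, among other outputs, the "change from RTs over time in HBsAg, HBeAg, HBV DNA and ALT" (SAP 5.4.1.2.1).

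Protocol 6.5.1 says that when all completion criteria are met on the Week 24 results, "treatment with NA will be stopped at the next scheduled visit (ie, FU Week 2"). Participants who come close at Week 24 and qualify on FU Week 2 results may, after consultation with the Sponsor, stop at FU Week 4. The secondary follow-up objective (Protocol section 3, SAP 1.1) covers both groups.

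For participants who complete treatment, SAP Table 3 ends the treatment period on the "Date of Week 24 study agent intake – 1 day" (or the cut-off date, if earlier) and starts follow-up at "End of treatment period + 1 day". SAP Table 4 lists Week 24 (target Day 169) as a treatment-period visit.

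**The concern.** An RT named after NA would naturally mark the last value on NA, so that change from it describes what happens off NA. The other two RTs are tied to their own drug's start or stop. The NA RT is tied to the start of the follow-up phase, and participants are still taking NA at that point.

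Two consequences follow. Change-from-NA-RT summaries mix an on-NA interval with the off-NA period; if HBsAg is still falling then, that fall is counted as if it came after NA was stopped. And restricting the RT to participants who met the criteria at EOT gives no NA reference to those who qualify on FU Week 2 results, although the objective includes them.

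There is also an ambiguity. Because Tables 3 and 4 place Week 24 in different phases, two programmers could pick different samples as the NA RT.

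**Working it through.** The documents state no figure for the gap between the NA RT and the NA stop, so there is none to reproduce. The check is calendar arithmetic.

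**Inputs**
- SAP Table 4 target days: Week 20 = Day 141, Week 24 = Day 169, FU Week 2 = FU Day 15, FU Week 4 = FU Day 29. All satisfy day = 7 × week + 1.
- Schedule of Activities: follow-up visits are scheduled from the Week 24 visit; windows are ±3 days at Weeks 20 and 24 and ±4 days in follow-up; samples are drawn before dosing.
- Protocol 6.5.1: NA stops at FU Week 2 (qualifying on Week 24 results) or FU Week 4 (qualifying on FU Week 2 results).

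**Which sample is the reference?** By Table 3, the treatment period ends one day before the Week 24 intake and follow-up starts one day later, which is the Week 24 intake date itself. The Week 24 sample carries that same date, so by date it is not before follow-up and the reference falls back to Week 20. By Table 4, Week 24 belongs to the treatment period and is the reference. The baseline rule in SAP 5.1.4 resolves same-day order by using date and time; the NA RT has no such clause.

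**Gap** = (169 − reference day) + (FU target day of NA stop − 1)

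| Reference | Stop at FU Week 2 | Stop at FU Week 4 |
|---|---|---|
| Week 24 | 0 + 14 = 14 days (2 weeks) | 0 + 28 = 28 days (4 weeks) |
| Week 20 | 28 + 14 = 42 days (6 weeks) | 28 + 28 = 56 days (8 weeks) |

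Only the first column applies to participants who have an NA RT: those who qualify at EOT stop at FU Week 2. With visit windows it becomes 14 ± 4 = 10 to 18 days, or 42 ± (3 + 3 + 4) = 32 to 52 days. The second column describes participants whom the definition leaves out.

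**Possible size on HBsAg.** Assume, for illustration only, an even fall of 2 log10 over 24 weeks: 2 / 24 = 0.083 log10 per week. Two weeks give 2 × 0.083 = 0.17 log10; six weeks give 6 × 0.083 = 0.5 log10. SAP 5.4.1.1.3 applies cut-offs of 0.3 and 0.5 log10 to change from RTs, so the first figure is below the smallest cut-off and the second equals one.

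**Overlap with the JNJ-3989 RT.** The last JNJ-3989 dose is at Week 24. On the Table 4 reading, a completer's NA RT and JNJ-3989 RT are therefore the same sample, and the NA RT adds no new reference value.

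**The case against.** The best defence is that the coherent reading gives a gap of only 2 weeks. Besides Table 4, SAP 1.2 has follow-up beginning after the Week 24 visit, and SAP 5.4.1.1.1 defines the completion criteria on Week 24 results, so meeting them at EOT must mean Week 24. This stands as the more sensible reading. It does not remove the Table 3 wording, and it still leaves the reference before the NA stop.

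Second, no JNJ-3989 is given after the Week 24 visit and PegIFN-α2a ends at Week 23 (Week 11 in Arm 3), so an on-treatment slope need not apply from Week 24 to FU Week 2. That is right, and the 0.17 log10 figure is only illustrative. Some continuing fall is plausible: Protocol 4.3 reports that in the Phase 1/2a study mean HBsAg reached its nadir 8 weeks after the last JNJ-3989 dose. But such carry-over would run past FU Week 2 as well, so moving the reference removes only its on-NA part. For HBV DNA, qualifying participants are already below 60 IU/mL or below LLOQ, which leaves little room for further decline.

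Third, the SAP never says that the NA RT measures change since the NA stop. That purpose is inferred from its name and from the other two RTs. The inference is fair but not certain.

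Fourth, stopping at FU Week 4 is a discretionary exception, so the omitted group may be small. The documents do not give its expected size.

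**Conclusion.** The point holds as a misaligned definition with limited reach. Under either reading, the NA RT precedes the planned NA stop: by 2 weeks on the Table 4 reading, or by 6 weeks if Table 3 is applied by date. Missing samples could lengthen either gap. FU Week 2 qualifiers have no NA reference although the secondary follow-up objective covers them.

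Three stronger conclusions that a reader might draw are not supported:
- **A gap of up to 8 weeks.** The 4- and 8-week gaps need a stop at FU Week 4, which applies only to participants who have no NA RT.
- **A definite fallback to Week 20.** This follows from one of two conflicting tables.
- **Distorted off-treatment efficacy results in general.** Off-treatment seroclearance, HBV DNA suppression and flares have their own definitions (SAP 5.4.1.1.4.2, 5.4.1.1.10, 5.4.1.1.14) and do not use the RT. The primary endpoint uses change from baseline.

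What is affected is the set of supplementary change-from-RT outputs: the HBsAg decline cut-offs, the continuous summaries and plots (SAP 5.4.1.2.1, 5.4.2.2.1), and the corresponding HBV RNA and HBcrAg outputs. SAP Table 13 items 45 and 46 still speak of stopping NA at Week 24, which suggests, without proving it, that the NA RT was not updated when the stop moved to FU Week 2 or FU Week 4. This is a minor point, worth correcting because the repair is easy.

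**What to change.** In SAP 5.1.6, define the NA RT as the last non-missing measurement up to and including the visit at which NA is first stopped under the completion criteria, before any NA re-treatment. Apply it to every participant who stopped NA on Week 24 or FU Week 2 results, and to those who discontinued JNJ-3989 early and then stopped NA under the criteria, as Protocol 6.5.1 allows.

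The rule should name the first stop visit rather than the last NA intake. For a re-treated participant the last intake comes after the restart. If no tablet is taken on the stop day, the last intake is the day before, and the sample from the stop visit would be lost.

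Reconcile Tables 3 and 4 so that the pre-dose Week 24 sample is assigned to the treatment period; this also settles what EOT means in the definition.

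The cost is a few lines of SAP text and matching programming, with no new data: quantitative HBsAg and HBV DNA are scheduled at FU Week 2 and FU Week 4. For those markers the planned on-NA gap falls to about zero. The Schedule of Activities appears to have no FU Week 2 sample for HBV RNA or HBcrAg, so for these two the reference for a FU Week 2 stop would remain Week 24, and a footnote should say so.

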### **5.1.7. Level of Significance**

For the primary efficacy endpoint analysis, the statistical comparison will be conducted using an exact binomial test against a fixed external control value of 2% at a one-sided Type 1 error rate of 0.05 and applying the Hochberg procedure for adjusting for multiple comparisons. For the comparisons between the intervention arms (Arms 1,2,3), the Mantel-Haenszel test adjusting for the stratification factors will be used in a secondary analysis to compare the primary endpoint between the intervention arms at a one-sided alpha level of 0.05 and applying the Hochberg procedure for multiple comparisons adjustment.

For all other efficacy analyses, only two-sided 90% CIs will be provided with no adjustment for multiplicity, unless otherwise specified.

### **5.1.8. Missing and Partial Dates Imputation Rules**

For analysis and reporting purposes, missing or partial dates in adverse event (AE onset date; AE end date), HBV diagnosis and infection dates, concomitant therapies (start date; end date) will be imputed according to the rules in the following subsections. The original, non-imputed, dates will be used only in listings.

### 5.1.8.1. Adverse Event Onset Date and Resolution Date

Partial AE onset dates will be imputed as follows:

- If the AE onset date is missing the day only, it will be set to:
  - The first day of the month when the AE occurred, if month/year of the AE onset date is different than the month/year of the first administration of study treatment date.
  - The day of the first study treatment administration, if the month/year of the AE onset date is the same as the month/year of the first study treatment administration but the month/year of the AE resolution date is different.
  - The earliest between the day of the first study treatment administration date and day of AE resolution date, if month/year of the AE onset are the same as both the month/year of the first study drug administration and the AE resolution date.
- If the AE onset date is missing both day and month, it will be set to the earliest of:
  - January 1 of the year of onset, as long as this date is on or after the first study drug administration.
  - Month and day of the first study treatment administration, if this date is in the same year of AE onset date.
  - December 31 if the AE onset date year is prior to the year of the first study drug administration.
  - The AE resolution date.
- Completely missing onset dates will not be imputed.

Partial AE resolution dates not marked as ongoing will be imputed as follows:

- If the resolution date of an AE is missing the day only, it will be set to the earliest of the last day of that month or the day of the date of death, if the participant died in that month.
- If the resolution date of an AE is missing both day and month, it will be set to the earliest of December 31 of that year or the day and month of the date of death, if the participant died in that year.
- Completely missing resolution dates will not be imputed.

### 5.1.8.2. HBV Diagnosis and Infection Dates

If the reported date is partially missing, the following imputation rules will be applied:

- the 15th of the month, if only the day is missing.
- the 30th of June, if only the year is available.
- No imputation if completely missing.

### 5.1.8.3. Concomitant Medication Dates

In case of partially missing concomitant medication start/end dates, the following imputation rules will be applied:

- the 15th of the month, if only the day is missing.
- the 30th of June, if only the year is available.
- If the imputed start date is after the concomitant medication end date, further adjustment of the imputed start date is required. It will be imputed as the concomitant medication end date.
- No imputation if completely missing.

If the medication was taken prior to study start (TP Day 1) based on eCRF question, and the imputed start date is after first treatment date, further adjustment of the imputed start date is required. It will be imputed as the day prior to first dosing date.

If the medication was taken after study start (TP Day 1) based on eCRF question, and the imputed start date is prior to first dosing date, the imputed start date will be further adjusted to be the first study treatment dosing date. The partially missing medication end date will be imputed following the rule described at the beginning of this section to ensure it is on or after first dosing date, and after its start date.

- In case of a completely missing start date, the concomitant therapy will be considered as having started before the trial, unless the eCRF indicating that the medication was taken after study start.
- In case of a completely missing end date, the concomitant therapy will be considered as ongoing at the end of the trial, unless the eCRF indicating not ongoing.

#### **5.1.8.4. Dates of Alcohol Consumptions**

In case of partially missing start/end dates, the following imputation rules will be applied:

- the 15th of the month, if only the day is missing.
- the 30th of June, if only the year is available.
- If the imputed start date is after the end date, further adjustment of the imputed start date is required. It will be imputed as the end date.
- If end date is completely missing and marked as Ongoing then impute with randomization date. Otherwise, no imputation if completely missing.

#### **5.1.9. Data Handling Rules**

Those measurements collected from screening visit to the end of study will be handled according to the following rules summarized in [Table 5](#).

**Table 5: Data Handling Rules for HBV Virology and Serology Assessments**

HBV parameter	LLOQ	ULOQ	Imputed Values	
			If value < LLOQ	If value > ULOQ
HBsAg	0.05 IU/mL	124,925.00 IU/mL w/o dilution  249,750.00 IU/mL with dilution	0.025 IU/mL (a)	137,417.50 IU/mL w/o dilution (b)  274,725.00 IU/mL (b) with dilution
HBeAg	0.11 IU/mL	1,400.00 IU/mL w/o dilution  7,000.00 IU/mL with dilution	0.055 IU/mL (a)	1,540.00 IU/mL (b) w/o dilution  7,700.00 IU/mL (b) with dilution
HBcrAg*	3.0 log 10 U/mL	7.0 log 10 U/mL w/o dilution  9.0 log 10 U/mL with dilution	2.7 log 10 U/mL	7.7 log 10 U/mL (b)(c) w/o dilution  9.9 log 10 U/mL (b) with dilution
HBV DNA	20 IU/mL	170,000,000 IU/mL w/o dilution	If target detected: 15 IU/mL If target not detected: 5 IU/mL	187,000,000 (b)(c) IU/mL w/o dilution
HBV RNA*	LLOQ = 2.939 log 10 cp/mL (i.e. 869 cp/mL)  LOD = 1.398 log 10 cp/mL (i.e. 25 cp/mL)	NAP	If <LOD or target not detected then 1.114 log 10 cp/mL (i.e. 13 cp/mL)	NAP
Anti-HBs	5 mIU/mL	10,000.0 mIU/mL	2.5 mIU/mL (a)	11,000.0 mIU/mL (b)

\* As new assays become available different data handling rules may apply.

Key: NAP=Not applicable

(a) LLOQ/2

(b) ULOQ+(ULOQ/10)

(c) If the original result > ULOQ, then take the re-test value (i.e. diluted result). If the diluted result is not available, use the imputed value indicated in this table

All other viral activity data with values <LLOQ which are not included in the data handling rules above will be imputed by the absolute value divided by 2.

## 5.2. Participant Dispositions

All the summaries will be done on the FAS analysis set unless specified otherwise.

Screened participants and reason for screen failures will be summarized overall.

The number of participants in the following disposition categories will be summarized throughout the study by intervention group and overall:

- Participants randomized
- Participants who received any study intervention (JNJ-3989, PegIFN- $\alpha$ 2a, NA)
- Participants in each study analysis phase
- Participants who completed the study
- Participants who discontinued any study intervention
- Reasons for discontinuation of any study intervention
- Participants who terminated study prematurely
- Reasons for termination of study

A listing of participants will be provided for the following categories:

- Participants who discontinued any study intervention
- Participants who terminated study prematurely
- Participants who were unblinded during the study period
- Participants who were randomized yet did not receive study intervention.

### 5.3. Primary Efficacy Endpoint

#### 5.3.1. Definition

The primary endpoint is the proportion of participants with a reduction of at least 2  $\log_{10}$  IU/mL in HBsAg levels from baseline at Week 24 (EOSI).

#### 5.3.2. Main Estimand for the Primary Endpoint

**Study Objective:** To evaluate the efficacy in terms of HBsAg changes from baseline for the treatment regimens of 24 weeks of JNJ-3989 + 24 weeks of NA + 12 or 24 weeks of PegIFN- $\alpha$ 2a (with immediate or delayed start of PegIFN- $\alpha$ 2a treatment), as compared to NA standard of care treatment.

**Scientific Question of Interest:** in HBeAg negative virologically suppressed adult population with chronic HBV infection

- a) Comparison vs fixed control: what is the benefit of JNJ-3989 + 24 weeks of NA + 12 or 24 weeks of PegIFN- $\alpha$ 2a in terms of reduction of at least 2  $\log_{10}$  IU/mL in HBsAg levels from baseline at Week 24 compared with fixed proportion 2% for NA (standard of care treatment)?
- b) Comparison amongst regimens: what is the benefit of JNJ-3989 + 24 weeks of NA + 12 or 24 weeks of PegIFN- $\alpha$ 2a in terms of reduction of at least 2  $\log_{10}$  IU/mL in HBsAg levels from baseline at Week 24 compared amongst regimens (Arm 1 versus Arm 2, Arm 1 versus Arm 3, and Arm 2 versus Arm 3)?

**A) Study Intervention:**

- Arm 1: JNJ-3989 for 24 weeks + NA for 24 weeks + PegIFN- $\alpha$ 2a for 24 weeks.
- Arm 2: JNJ-3989 for 24 weeks + NA for 24 weeks + PegIFN- $\alpha$ 2a from Week 12 till Week 24.
- Arm 3: JNJ-3989 for 24 weeks + NA for 24 weeks + PegIFN- $\alpha$ 2a from baseline till Week 12.

**B) Study Population:** HBeAg-negative chronic HBV-infected adult patients who are virologically suppressed by being treated with NA.

**C) Variable:** Response status defined as participants with reduction of at least 2 log10 IU/mL in HBsAg levels from baseline at Week 24 (responders) as in Section 5.3.1.

**D) Intercurrent events:**

- Treatment discontinuation prior to Week 24: if the participant discontinued treatment prior to Week 24 then s/he will be considered non-responder (composite strategy).
- Major protocol deviations affecting efficacy: Table 13 identifies the deviations considered intercurrent event. Participants with such deviations and who have missing data for the endpoint will be considered as non-responders (composite strategy). For all other deviations not considered intercurrent events, the data are used regardless of the occurrence of major protocol deviations (treatment policy strategy).
- Deaths prior to Week 24 are handled in a composite strategy as participants who die prior to Week 24 will be considered as non-responders.

